#### ***Pharmacokinetics***

ELX-02 given SC was rapidly absorbed with a median time to maximum concentration ( $t_{max}$ ) of about 0.5-1.0h.  $AUC_{0-\infty}$  changed linearly with ELX-02 dose (24-fold increase for a 25-fold dose increase) and  $C_{max}$  changed in a quasi proportional way with ELX-02 dose as significant Dose effects were seen (17-fold increase for a 25-fold increase). The apparent terminal half-life was 2 to 4h in the dose range tested (0.3 mg/kg to 7.5 mg./kg).

Plasma concentration profiles were linearly and proportionally related to the dose administered. ELX-02 had a rapid elimination phase and a slower distribution phase. ELX-02 was excreted and recovered almost quantitatively in the urine during the first 12 hours.

[figure not shown]
[figure not shown]

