### **9.2. Pharmacokinetic Analysis**

Pharmacokinetic parameters of ELX-02 ( $C_{max}$ ,  $t_{max}$ ,  $AUC_t$ ,  $AUC_{24h}$ ,  $AUC_{48h}$ ,  $AUC_{72h}$ ,  $AUC_{inf}$ ,  $t_{1/2}$ ,  $Vd/F$ , and  $CL/F$ , ) will be summarized by descriptive statistics by dose group and day of administration (sample size, mean, median, standard deviation, CV%, minimum and maximum, geometric mean and geometric CV%, when applicable).

Steady-state achievement will be evaluated by visual inspection of predose (and 1h postdose) concentrations figures.

For each of the PK parameters  $C_{max}$  and AUCs, the dose linearity will be assessed using a power model, including the log-transformed PK parameters as dependent variables and the log-transformed dose, day and dose\*day as fixed effects. The slope for log-transformed dose ( $\beta$ ) will be estimated with its 90% confidence interval to examine dose proportionality. The  $t_{max}$  will be compared between dose groups and days using the appropriate non-parametric tests.

Plots of individual subject time-course profiles of ELX-02 after the administration will be presented by subject and day of administration in linear and semi-logarithmic scales. Figures enclosing all subjects for each dose and day of administration will be provided. Mean (SD) plasma concentrations obtained for each administration mode and drug dose will be plotted on

linear and semi-logarithmic scales. Through (predose and 1h postdose) figures will also be presented individually and as average.

The following parameters will be calculated based on ELX-02 urine concentrations: urinary excretion (Ae) of ELX-02 (in mass and %dose - fe) for each collection interval, cumulated urinary excretion (in %dose) for each collection interval, total excretion (in %dose) and renal clearance (using the AUC and Ae for the same time interval).

Actual sampling times will be used for PK analysis (when actual sampling times are not available, planned times will be used instead).

PK analysis will be performed on the PK population (i.e. enrolled subjects, with analyzable PK data and without relevant deviation interfering with the PK evaluations). The PK parameters will be calculated with WinNonlin Phoenix 6.2 (or later) software using non-compartmental analysis method.

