1. INFORMATION FROM THE STUDY PROTOCOL

1.1. Introduction and Objectives

1.1.1. Introduction

ELX-02, characterized as a eukaryotic ribosomal selective glycoside (ERSG), is a small molecule, new chemical entity being developed by Eloxx Pharmaceuticals for the treatment of genetic diseases caused by nonsense mutations. Nonsense mutations generating premature termination codons account for approximately one third of all genetic diseases. Nonsense mutations are a genetic mutation in a deoxyribonucleic acid (DNA) sequence that results in a shorter, unfinished protein product. Consequently, most nonsense mutations result in nonfunctional proteins (Mendell, 2001; Keeling, 2006). Examples of genetic diseases where nonsense mutations are part of their phenotype include Rett syndrome, Mucopolysaccharidosis type I (Hurler syndrome), Duchenne muscular dystrophy, and cystic fibrosis.

Across a series of pharmacology studies, the translational read-through capabilities of ELX-02 have been tested in in vitro cell models and in vivo animal models. ELX-02 induced expression of functional proteins with pharmacodynamic and behavioral effects with a satisfactory window of safety in several cellular and animal models of genetic disease caused by nonsense mutations, including, cystic fibrosis (CF) and cystinosis. More information on ELX-02 can be found in the Investigator's Brochure.

Eloxx Pharmaceuticals has completed two Phase 1a, single-center, randomized, double-blinded placebo-controlled single ascending dose studies in healthy human subjects. After single subcutaneous (SC) administration, ELX-02 was generally well tolerated at doses ranging from 0.3 to 7.5 mg/kg without severe or serious drug-related adverse events (AEs). The mean terminal apparent half-life ranged between 2 and 8 hours. AUC_{inf} showed dose linearity and C_{max} approximate proportionality.

This multicenter study was initiated to assess the safety, tolerability and pharmacokinetics (PK) of ELX-02 in healthy human subjects receiving multiple escalating doses (ranging from 0.1 to 5.0 mg/kg) via SC injection(s) in a randomized, double-blinded, placebo-controlled design.

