1.2. Study Design

1.2.1. Synopsis of Study Design

This is a Phase 1, randomized, double-blind, placebo-controlled, third party open (i.e. pharmacist), multiple dose escalation study to evaluate the safety, tolerability and PK of SC administered ELX-02 in independent consecutive cohorts of healthy subjects.

The investigational drug, ELX-02, is formulated as a solution for SC injection, containing 200 mg/mL. The placebo control will consist of a SC injection of normal saline at matching volumes.

The study is designed to include at least 5 cohorts of 9 subjects each, including both males and females. Subjects will be randomized to receive multiple doses of ELX-02 or placebo at a ratio of 2:1 in each cohort; 6 subjects will receive ELX-02 and 3 will receive placebo for a total of up to 63 subjects. Study drug will be administered SC twice a week for 9 doses and dose levels planned in the protocol for each cohort are described below:

- Cohort 1: ELX-02 0.1 mg/kg or placebo
- Cohort 2: ELX-02 0.3 mg/kg or placebo
- Cohort 3: ELX-02 1.0 mg/kg or placebo
- Cohort 4: ELX-02 2.5 mg/kg or placebo
- Cohort 5: ELX-02 up to 2.5 mg/kg or placebo
- Cohort 6: ELX-02 2.5 to 5.0 mg/kg or placebo
- Cohort 7: ELX-02 up to 5.0 mg/kg or placebo

Dose escalation to the next cohort will not be performed until 14 days after the last subject's last dose in the previous cohort, to allow for detection of unanticipated delayed AEs.

The decision to proceed to a higher dose level will be following the recommendations of both the general Data Safety Monitoring Board (DSMB) and the Auditory and Vestibular Data Safety Monitoring Board (AVDSMB) based on the dose-escalation stopping rules. The DSMB and AVDSMB recommendation to proceed to a higher dose will be based on review of the blinded safety data, any available blinded PK data, and the results of audiologic tests and questionnaires. The next cohort will be dosed after the DSMB and AVDSMB have evaluated the available data and have recommended to escalate.

The principles of dose escalation, determination of dose limiting toxicity (DLT) and MTD, are detailed in Protocol Section 3.2.

Study duration will be approximately 12 weeks for each subject including a screening period of up to 6 weeks, treatment period of 4 weeks, and 2 weeks for final safety follow-up. Subjects will receive in-patient treatment in the Clinical Pharmacological Unit (CPU) for approximately 8 days throughout the treatment period.

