4.3.1. PK Concentrations and Parameters

4.3.1.1. Plasma PK Concentrations

Blood samples to determine ELX-02 concentrations in plasma will be drawn on Day 1 and Day 29 at the following nominal time points:

- Predose, 15 min (\pm 2 min), 30 min (\pm 5 min), 45 min (\pm 5 min), 1h (\pm 5 min), 3h (\pm 15 min), 6h (\pm 15 min), 12h (\pm 30 min), 24h (\pm 1h), 36h (\pm 1h), 48h (\pm 1h), 72h (\pm 1h).

and on Days 4, 8, 11, 15, 18 and 22 at the following nominal timepoints:

- Predose and 1h postdose (\pm 5 min).

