- $t_{1/2}$: Apparent elimination half-life associated with the terminal rate constant (λ_z), calculated as $\ln 2 / \lambda_z$ (Day 1 and Day 29).
- λ_z : Terminal elimination rate constant is calculated using clearance (CL/F) and volume of distribution (V_d/F) ($\lambda_z = (CL/F)/V$).
- V_d/F : Apparent volume of distribution (Day 1 and Day 29). V_d/F (or V_z) will be calculated based on terminal phase using the equation “Dose/ $\lambda_z \cdot AUC_{\text{inf}}$ ”, uncorrected

for fraction absorbed.

- CL/F: Apparent plasma clearance, uncorrected for fraction absorbed (Day 1 and Day 29).
- Rac_(AUC): Accumulation ratio, calculated as AUC_{72h} Day29/AUC_{72h} Day 1.
- Rac_(C_{max}): Accumulation ratio, calculated as C_{max} Day29/C_{max} Day 1.

Additional pharmacokinetic parameters may be calculated as appropriate.

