4.3.2. Dose Proportionality Assessment

Differences in PK profiles between final diluted injection concentrations (50 vs 100 mg/mL) will be explored using the figures (Section 4.3.3) and the “by concentration” tables. AUC and C_{max} will be evaluated using the ratio with its 90% confidence interval to compare Cohort 3 vs 5 and Cohort 4 vs 6. The elimination half-life, t_{1/2}, will be evaluated using the Kruskal-Wallis test. If no apparent differences in the PK profiles and PK parameters between the injection concentrations are observed, the PK data from two different cohorts with the same dose will be pooled together for assessing dose proportionality. Otherwise, dose proportionality will be assessed using the data from Cohorts 1, 2, 5, 6, and 7 in which the lower diluted injection concentration (50 mg/mL) was administered.

Dose proportionality will be assessed using a power model separately on Day 1 and Day 29, including the log-transformed PK parameters (C_{max} , AUC_t , and AUC_{inf}) as the dependent variables and the log-transformed dose as the fixed effect. Individual PK values will be used to perform a least-squares linear regression analysis, using the formula:

$\log_{pkvar} = A + \beta \times \log_{dose}$, where:

- ' \log_{pkvar} ' represents the natural log transformed C_{max} , AUC_t , and AUC_{inf} .
- ' \log_{dose} ' represents the natural log transformed dose.

The slope for log-transformed dose (β) will be estimated with its 90% confidence interval to examine dose proportionality. The PROC REG procedure will be used in SAS in the following data step:

```
PROC REG DATA=pkparam alpha=0.10; MODEL log_pkvar = log_dose / CLB; RUN;
```

The t_{max} will be compared between dose groups and days (Days 1 and 29) using the Kruskal-Wallis one-way analysis of variance (ANOVA). P-values based on the Kruskal-Wallis test will be presented.

Additional statistical analysis may be performed. If applicable, steady state will be informally assessed via a visual inspection of the figures of predose and 1-hour postdose plasma concentrations vs time (day).

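### The visual steady-state check on predose and 1 h concentrations says little about change in PK over four weeks, and the SAP plans no interval for the Day 29 versus Day 1 exposure ratios that would

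*SAP*

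**What the plan says.** Protocol 9.2 states: "Steady-state achievement will be evaluated by visual inspection of predose (and 1h postdose) concentrations figures". SAP 4.3.2 keeps this, qualifies it as applying only if applicable, and says that "steady state will be informally assessed via a visual inspection of the figures of predose and 1-hour postdose plasma concentrations vs time (day". Neither document gives a numerical criterion.

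The regimen is in SAP 1.2.1: "Study drug will be administered SC twice a week for 9 doses". Protocol 7.1 puts the doses on Days 1, 4, 8, 11, 15, 18, 22, 25 and 29, so the gaps alternate between 72 and 96 h. On half-life, SAP 1.1.1 says: "The mean terminal apparent half-life ranged between 2 and 8 hours". Protocol 1.2.2 says: "The apparent terminal half-life was 2 to 4h in the dose range tested". The same protocol section gives a median tmax "of about 0.5-1.0h".

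Full 72 h profiles are taken on Days 1 and 29. From these, SAP 4.3.1.2 derives AUCs, Cmax, half-life, CL/F and two accumulation ratios, one of them "Accumulation ratio, calculated as AUC_{72h} Day29/AUC_{72h} Day 1". SAP 4.3.1.4 adds renal clearance on both days. SAP 4.3.3 summarises all of these with geometric mean and geometric CV.

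Protocol 9.2 put day and dose-by-day in the power model. SAP section 5 removes both because each day is fitted separately. Predose and 1 h sampling is listed in SAP 4.3.1.1 as "and on Days 4, 8, 11, 15, 18 and 22 at the following nominal timepoints", without Day 25, although protocol 7.1 and 7.2 collect those samples on that day.

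**The concern.** Multiple-dose PK is a primary objective. Protocol 1.1.2 describes a drug excreted unchanged by the kidney in proportion to creatinine clearance, and nephrotoxicity is an adverse event of interest. The time-dependent change most worth excluding is therefore a fall in clearance over the dosing period.

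The two quantities chosen for inspection are badly placed to show it. A predose sample is taken many half-lives after the previous dose. A 1 h sample is close to tmax, where absorption and volume set the level. The measurements that do respond are the paired Day 1 and Day 29 profiles, and the plan does not connect them to the steady-state statement. The risk is a conclusion about steady state or time-invariance that rests on displays with little power to contradict it.

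**Working it through.** The documents give no power, error rate or precision figure for this point, so there is no planned number to reproduce.

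**Inputs from the documents.** Half-life 2 to 8 h (SAP 1.1.1) or 2 to 4 h (protocol 1.2.2); tmax 0.5 to 1.0 h; gaps of 72 and 96 h; 6 active subjects per cohort and 7 cohorts.

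**Assumptions.** One compartment with first-order absorption, V and F fixed, ka solved to give tmax of 0.5, 0.75 or 1.0 h, clearance falling by one third, and within-subject CV of 10 to 30%. LLOQ is not stated.

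**1. Accumulation with constant clearance.** The fraction left after 72 h is 2^(−72/t½): 1.5×10⁻¹¹ at 2 h, 3.8×10⁻⁶ at 4 h and 0.20% at 8 h. Expected accumulation, 1/(1 − fraction left), is 1.000 to 1.002.

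**2. Response to a one-third fall in clearance.** The concentration is proportional to ka/(ka−k) × (e^(−kt) − e^(−ka·t)), with k = ln2/t½. Example for t½ 4 h and tmax 0.75 h, where ka = 4.52 and k goes from 0.1733 to 0.1155:
- C1h before: 1.0399 × (0.8409 − 0.0109) = 0.863
- C1h after: 1.0262 × (0.8909 − 0.0109) = 0.903
- ratio 1.046, while AUC rises by 1/(2/3) = 1.50

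Over the range of tmax, with all nine doses superposed:

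| t½ | C1h ratio | Cmax ratio | AUC72h ratio |
|---|---|---|---|
| 2 h | 1.08–1.10 | 1.05–1.09 | 1.50 |
| 3 h | 1.05–1.07 | 1.03–1.06 | 1.50 |
| 4 h | 1.04–1.05 | 1.02–1.05 | 1.50 |
| 8 h | 1.03 | 1.02–1.03 | 1.48 |

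Without carry-over from the preceding dose, the 8 h C1h ratio is 1.02 and AUC72h is still 1.48.

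**3. Predose values after the same fall.** For t½ of 2 to 4 h, the 72 h value is at most about 0.03% of Cmax and the 96 h value at most about 0.002%. At 8 h the half-life becomes 12 h. The fraction left goes from 2^(−9) = 0.20% to 2^(−6) = 1.6% after 72 h (8-fold), and from 2^(−12) = 0.024% to 2^(−8) = 0.39% after 96 h (16-fold).

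**4. Reading the predose plot.** The alternating gaps alone change predose by 2^(24/t½) with constant clearance: 8-fold at 8 h and 64-fold at 4 h. SAP 4.3.3 also drops BLQ values from concentration summaries, so mean troughs rest on quantifiable values only.

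**5. Precision of a paired Day 29/Day 1 ratio.** The 90% half-width on the log scale is t(0.95, n−1) × √2 × σw/√n, with σw = √ln(1+CV²). At CV 15% and n=6: 2.015 × 1.414 × 0.149/2.449 = 0.174, a factor of e^0.174 = 1.19. For all 7 × 6 = 42 active subjects the factor is 1.06. Over CVs of 10 to 30% at n=6, the chance that the 90% CI excludes 1 is about 1.00 to 0.66 for a true AUC ratio of 1.5. For a 1 h ratio of 1.06 it is about 0.23 to 0.12.

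**The case against.** The strongest reply is that the plan as a whole already covers a clearance change. Rac(AUC) would be near 1.5 and CL/F about one third lower, both in planned tables. SAP 4.3.3 overlays Day 1 and Day 29 profiles. Given n, geometric mean and geometric CV, a reader could compute the interval unaided. All of this stands, and it limits the point to a missing interval and a missing link to the conclusion.

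It is also fair that flat plots are the right answer when clearance is constant. The check is uninformative, not wrong.

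Three stronger readings are tempting, and the documents do not support them.
- A reader might infer that the rule would always declare steady state. There is no rule, only an informal inspection with no criterion. At an 8 h half-life, troughs rise 8- to 16-fold and could show on the semi-log plots planned in SAP 4.3.3 if above LLOQ. The slower phase described in protocol 1.1.2 could also show; an assumed 48 to 72 h phase would raise predose about 1.4- to 1.7-fold on like intervals.
- A reader might infer that renal harm would go unnoticed. Serum creatinine, KIM-1 and clusterin are monitored separately.
- A reader might infer that the Day 25 data are lost. The protocol collects them, and SAP 4.3.1.2 defines the predose and 1 h values at each dosing. The omission in SAP 4.3.1.1 is clerical.

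The reply does not answer the loss of between-day inference. Fitting each day separately does make the day terms unnecessary for the slope. It also leaves the Kruskal-Wallis test on tmax as the only formal comparison of days, and none for exposure.

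**Conclusion.** The point holds as a worthwhile improvement, not as a defect that would hide a large effect. The steady-state displays carry little information on time-dependent PK: for a one-third fall in clearance, C1h moves about 2 to 10% against 48 to 50% for AUC72h, and predose is practically zero over 2 to 4 h half-lives. The informative Day 29/Day 1 quantities are planned, but without an interval and without a stated role in the conclusion.

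The sizes rest on the one-compartment model, fixed V and F, and the illustrative one-third fall. Predose behaviour towards an 8 h half-life, or with a slow phase, depends on an LLOQ that the documents do not give.

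**What to change.** In SAP 4.3.2, base the accumulation or time-invariance statement on within-subject log(Day 29) minus log(Day 1). Report geometric mean ratios with 90% CIs for AUC and Cmax, and optionally for CL/F and CL_R.
- AUC72h is already used in Rac. AUC24h is an alternative if late samples are mostly BLQ, but it responds less at a long half-life: ignoring absorption, 1.5 × 0.75/0.875 = 1.29 at 8 h.
- Report by dose, with the estimate pooled over doses as supportive only, because a change confined to the high doses would be diluted.
- Keep the C0h and C1h figures as supportive, and compare predose values within like gaps (72 h with 72 h, 96 h with 96 h).
- Add Day 25 to the list in SAP 4.3.1.1, and reconcile the two half-life ranges.

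The cost is a few lines of text and one table from data already collected. Intervals at n=6 will be wide, about ×/÷ 1.19 at an assumed 15% CV, so the result should be read as estimation.

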4.3.3. Pharmacokinetic Data Reporting

Tables:

All plasma and urinary PK concentrations will be summarized by dose, final diluted injection concentration, day, and timepoint using descriptive statistics (number of subjects, mean, SD, median, coefficient of variance [CV%], minimum and maximum). All PK concentration and descriptive statistic values will be reported to 3 decimal places.

All plasma and urinary PK parameters will be summarized by dose, final diluted injection concentration, and day using descriptive statistics (number of subjects, mean, SD, median, CV%, minimum and maximum, geometric mean, and geometric CV%). All PK parameters and descriptive statistic values will be reported to 3 decimal places, with the exception of the individual t_{max} values, which will be reported to 2 decimal places. Footnotes will include information on parameters not included in summaries and the reasons for not including.

All BLQ, zero, and missing values of PK parameters will not be included in concentration and parameters summary calculations. If the number of non-BLQ, non-zero, and non-missing values are less than 3 in a summarization group, summary statistics will not be calculated.

Listings:

Individual plasma PK sample collection times will be listed by cohort, and will include details about subject number, cohort, dose, day, nominal sample time point, actual sample time point and concentration in the PK population. If any subjects are excluded from the PK population, a separate listing will be produced for these subjects if PK parameters are calculable.

Individual urine PK sample collection times will include details about subject number, cohort, dose, scheduled urine collection interval, actual start and end time of urine collection interval, urine volume collected in the urine collection interval, and concentration in the PK population.

All values will be reported to 3 decimal places, with the exception of the individual t_{max} values,

which will be reported to 2 decimal places.

All BLQ concentrations or missing data will be labeled as such in the concentration data listings.

Figures:

Plasma PK concentration and PK parameter figures:

- Subject profile for plasma concentration-time will be presented graphically on a linear and semi-log scale for the PK population (overlaid Day 1 and Day 29, including C_{0h} and C_{1h} on each scheduled day between Day 1 and Day 29).
- Grouped individual plasma concentration versus nominal time will be presented (Spaghetti Plots) on the linear and semi-log for the PK population (by cohort, separate Day 1 and Day 29 plots).
- Arithmetic mean ($\pm SD$) plasma concentration vs nominal time profiles will be presented graphically on a linear and semi-log scale (no SD for semi-log plot) for the PK population (by cohort, separate Day 1 and Day 29 plots, all cohorts on one plot).
- Grouped individual predose and 1h postdose plasma concentration vs nominal time from Day 1 through Day 29 will be presented (Spaghetti Plots) on the linear and semi-log scale for the PK population (by cohort).
- Mean ($\pm SD$) predose and 1h postdose plasma concentration vs nominal time from Day 1 through Day 29 will be presented on the linear and semi-log scale (no SD for semi-log plot) for the PK population (by cohort).
- Additional PK plots (by dose): Day 1 and Day 29 where applicable C_{max} , t_{max} , $t_{1/2}$, AUC_{24h} , Cl/F , V_d/F vs dose.

Urine PK parameter figures:

- Subject profile for amount excreted over time will be presented graphically on a linear and semi-log scale for the PK population (overlaid Day 1 and Day 29). A dashed line representing individual subject dose will be included on each plot.
- Grouped individual amount excreted versus nominal time will be presented (Spaghetti Plots) on the linear and semi-log for the PK population (by cohort, separate Day 1 and Day 29 plots).
- Arithmetic mean ($\pm SD$) amount excreted vs nominal time profiles will be presented graphically on a linear and semi-log scale (no SD for semi-log plot) for the PK population (by cohort, separate Day 1 and Day 29 plots, all cohorts on one plot).
- Additional urine PK plots (by dose), including but not limited to plasma CL/F vs CL_R , may be included as appropriate.

Details of any deviations from the planned analysis will be documented in the PK report.

